Additionally, advances in measurement techniques and an understanding of ocular physiology suggest the need for updated normative data that reflect current population characteristics and incorporate modern assessment methodologies.

Given these limitations, there is a pressing need to establish population-specific normative data for the field of binocular single vision in Singapore's adult population. This would not only provide more relevant reference values for clinical assessment but also potentially improve the accuracy of diagnosis and monitoring of various ocular conditions in our local context.

Study Objectives

The primary purpose of this pilot study is to address these gaps in current clinical practice through two main objectives. First, we aim to establish the normative range of the field of binocular single vision specifically for adults in Singapore, creating a locally relevant reference

standard. This will provide clinicians with more appropriate benchmarks for assessing their patients.

Secondly, we seek to determine whether a significant difference exists between these local normative values and the currently used standards established by Feibel & Roper-Hall in 1974. We hypothesise that there will be a significant difference in the normative range of the field of binocular single vision in our current adult population in Singapore compared to the historical standards. This hypothesis is based on the understanding that genetic, environmental, and temporal factors may influence ocular characteristics.

The findings from this study could have substantial clinical implications. If significant differences are identified, it would justify the adoption of new, population-specific normative values for clinical practice in Singapore. This could lead to more accurate assessment and monitoring of subjects, potentially improving the quality of eye care delivered to our population. Furthermore, this study could serve as a model for other Asian countries to establish their population-specific normative values, contributing to the broader field of ophthalmology in the region.

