2. STUDY DESIGN

This research will be conducted as a single-centre, pilot study at Tan Tock Seng Hospital, designed as an observational investigation regulated under the Human Biomedical Research Act (HBRA) of Singapore. This study will employ a cross-sectional design, with each participant completing all assessments in a single visit lasting approximately 60 minutes. This approach has been chosen to minimise participant burden while ensuring comprehensive data collection.

The study will span a total duration of one year, with active data collection scheduled from 1 November 2025 to 31 October 2026. This timeline allows for adequate recruitment, data collection, and subsequent analysis while accounting for potential scheduling challenges and the need for careful quality control of the collected data. The single-visit design also helps minimise dropout rates and ensures consistency in data collection procedures.

Study Design:

Study population: This study aims to recruit a balanced sample of adult participants from Singapore's population, with a target enrolment of 32 participants, equally distributed between males and females (16 of each gender) and of Asian descent. This sample size has been

carefully determined to provide sufficient statistical power while remaining feasible within the study's resources and timeline.

Participants will be recruited primarily by word of mouth at the TTSH Ophthalmology Specialist Outpatient Clinic's, focusing on accompanying next-of-kin of existing patients, TTSH staff members, or any other available healthy volunteers after meeting the inclusion and exclusion criteria. The recruitment process will be conducted with careful attention to avoiding any coercion or undue influence, particularly in cases involving dependent relationships. All potential participants will be given adequate time to consider their participation and will be required to provide informed consent in the presence of a witness in compliance to the Declaration of Helsinki, as well as other prevailing laws and guidelines regulating clinical research.

Inclusion Criteria:

1. Age: 21 to 59 years old
2. Gender: Males or females
3. Ethnicity: Asian descent.
4. Language comprehension: Able to understand verbal spoken instructions in:
 - British/American English
 - Mandarin Chinese
 - Bahasa Melayu
5. Protocol compliance: Ability to comply with the study protocol, as determined by the investigator's judgment

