6. Consent capacity: Must be able to understand and provide informed consent, with signed informed consent form required before any study assessments

Exclusion Criteria:

1. Communication barrier: Unable to understand verbal spoken instructions
2. Medical history:
 - Any facial trauma
 - Any ocular trauma
 - Any head trauma
 - Any history of ocular disease
 - Any history of ocular surgery
 - Systemic condition(s)

3. Near visual acuity:

- Right eye & Left eye monocularly, binocularly unaided near vision: worse than N6 at 40cm from participant's nose

4. Ocular alignment:

- Prism cover test at near (30cm) of equal or greater than 10 prism diopters at these positions of gaze:

- Primary gaze
- Right gaze
- Left gaze
- Up gaze
- Down gaze

5. Extraocular movement:

- Extraocular movement of over-action or under-action of equal or greater than 0.5 in any of the nine cardinal positions of gaze

6. Confrontational Visual field:

- Abnormal monocular visual field on confrontational visual field test

7. Hess chart test

- Abnormal or asymmetry in pattern of extraocular muscle action in Hess chart test

8. Pregnant woman will be excluded from this study.

Study Procedure:

This cross-sectional study will involve 1 study visit.

Pre-specified clinical outcome: The primary outcome is the establishment of a normative range of field of binocular single vision measurements in Singapore adults. These measurements will be taken using the Takagi MT-325UD Projection Perimeter. The secondary outcome is the comparison with the normal boundary of the established field of binocular single vision by Feibel & Roper-Hall (1974) and the analysis of any significant differences between the two sets of measurements.

Clinical Validation will be a cross-sectional study design to determine the normative range of the field of binocular single vision measurements in participants who are Singapore adults focusing on accompanying next-of-kin of existing participants and TTSH staff members after meeting the inclusion and exclusion criteria.

Research Procedures:

1) *Medical history assessment*

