Extraocular muscle function will be examined by having the participant follow a fixation target through the nine cardinal positions of gaze. The examiner will assess and grade any overaction or underaction of the extraocular muscles using a standardized scale, where 0 represents normal movement. Participants demonstrating overaction or underaction equal to or greater than 0.5 units in any direction will be excluded from the study. The examination will be conducted methodically, ensuring smooth pursuit movements are carefully observed and documented.

5) Confrontational Visual Field Testing

Monocular confrontational visual field testing will be performed separately for each eye. The examiner will sit at one meter distance, directly facing the participant at eye level. Each quadrant of the visual field will be tested systematically using standardized targets, while the participant maintains fixation on the examiner's nose. Any abnormality in the visual field will be documented and will result in exclusion from the study. The testing sequence will remain consistent for all participants to ensure standardization of the assessment.

6) Hess Chart Testing

The Hess chart test will be conducted using a standard Hess screen at the recommended testing distance. This test will evaluate the action of each extraocular muscle, with results plotted on the Hess chart. The examiner will assess for any asymmetry or abnormality in the pattern of extraocular muscle action. Any abnormal findings on the Hess chart will be documented in detail and will result in exclusion from the study. The test will be performed following standardized protocols to ensure consistency and accuracy of results.

7) Field of binocular single vision

Participants perform the field of binocular single vision test binocularly and pursue a single round light stimulus presented in the bowl of the Takagi MT-325UD Projection Perimeter, and participants will need to look and follow through the single light stimulus as it moves throughout the bowl, and participants will press the buzzer if two distinct light stimuli are seen. Scores will be recorded and plotted on the recording sheet based on participants' responses during the test. Eye dilation will not be required for this research study.

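### The protocol recruits hospital staff at the eye clinic and does not rule out study-team members or staff who perform or read this test, although the outcome is the participant's own response

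*Protocol*

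**What the plan says.** **Who is recruited.** Under Study population (section 2, Study Design), participants are "recruited primarily by word of mouth at the TTSH Ophthalmology Specialist Outpatient" Clinic, "focusing on accompanying next-of-kin of existing patients, TTSH staff members, or any other available healthy volunteers". The Clinical Validation paragraph names staff again: "focusing on accompanying next-of-kin of existing participants and TTSH staff members after meeting the inclusion and exclusion criteria". Neither statement limits the department, the role or the number of staff.

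**Who is excluded.** The eight exclusion criteria cover communication, medical history, near acuity, alignment, eye movement, confrontation field, the Hess chart and pregnancy (the last item reads "Pregnant woman will be excluded from this study"). None concerns occupation, experience of the test or membership of the study team. The nearest discretionary criterion is inclusion item 5: "Ability to comply with the study protocol, as determined by the investigator's judgment". It concerns compliance, and someone who runs the test would meet it easily.

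**How the outcome arises.** In Research Procedures, item 7, the participant follows a moving light and "participants will press the buzzer if two distinct light stimuli are seen". Scores are plotted from those responses. The item describes no masking, repeat or catch trial.

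**What it is compared with.** The Background says that clinicians, including those in Singapore, rely on the 1974 boundary as the gold standard. The Study Objectives then state: "We hypothesise that there will be a significant difference in the normative range of the field of binocular single vision".

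**The concern.** The participant decides where the field ends. A person who runs or reads this test in daily work can be expected to know where it is supposed to end, and a member of the study team also knows the hypothesis. Neither is a naive observer.

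Both objectives are exposed. Responses drawn towards the 1974 limit would make the local range look tighter than it is, or hide a real departure from 1974. Responses drawn away from it would produce a departure that is not there. The Study Objectives say that a significant difference would justify adopting new normative values, so the result is meant to inform practice, and with 32 participants a handful of informed ones carry weight.

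The one safeguard in the recruitment text that bears on dependent relationships concerns coercion and undue influence in consent. It protects voluntariness, not the measurement.

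**Working it through.** **1. The plan's own figure.** Inputs from the Sample size calculation: SD 6 (literature range 5.3 to 6.9), precision 2.2, 95% confidence.

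- n = (1.96 × 6 / 2.2)² = 28.57, rounded up to 29, as stated.
- Half-width at n = 29: 1.96 × 6 / √29 = 2.18.
- The total of 32 matches 29 × 1.10 = 31.9 (29 / 0.90 would give 33). The point does not depend on this.

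**2. Shift of the mean.** The documents give neither the number of informed participants, k, nor the shift, b, in their reported limit. Both are assumptions here. The protocol also names no unit for the SD, so b is taken to be on the same scale. Mean shift = (k / 29) × b.

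| k of 29 | b = 2 | b = 4 | as a share of 2.2 |
|---|---|---|---|
| 3 | 0.21 | 0.41 | 9% to 19% |
| 8 | 0.55 | 1.10 | 25% to 50% |
| 16 | 1.10 | 2.21 | 50% to 100% |

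The last two rows need roughly a quarter to a half of the sample to be informed, which nothing in the protocol suggests.

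**3. Drawn away from the 1974 limit.** Suppose that the true local mean equals the 1974 limit and that all informed participants move the same way. A two-sided one-sample t-test at 5% (n = 29, SD 6) then rejects with these probabilities:

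- k = 3: 5.4% (shift 0.21) to 6.5% (shift 0.41).
- Net shift of 1 unit: 14%.
- Net shift of 2 units: 41% with the SD held at 6. If the 2 units come from half the sample shifting by 4, the mixture SD is √(36 + 0.25 × 16) = 6.32 and the figure is 38%.

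**4. Drawn towards the 1974 limit.** Suppose instead that informed participants simply reproduce the limit.

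- If the limit lies at the group mean, the mean does not move but the SD becomes 6 × √(1 − k/29): 5.68 for k = 3 and 5.11 for k = 8. The half-width of a 95% reference range (1.96 × SD) falls from 11.76 to 11.14 or 10.01.
- If the true mean differs from the limit by D, the observed difference becomes (1 − k/29) × D: 26/29 = 90% of D for k = 3, and 21/29 = 72% for k = 8.

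The two directions therefore have opposite consequences, and mixed directions partly cancel.

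**The case against.** **The risk is permitted, not planned.** The protocol says hospital staff, meaning the whole hospital, beside relatives and, under Study population, other volunteers. It never says that orthoptists, eye-clinic staff or investigators will take part. This stands: a reader might infer that the sample will be drawn largely from eye-clinic colleagues, and the documents do not support that.

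**The mechanism is not shown.** Knowing a limit on a chart does not prove that someone can reproduce it while following a light in the bowl. The hypothesis names no direction, and what other participants are told about it cannot be seen. This also stands, and it is why the effect may be small.

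**The large error rates are conditional.** The 14% and 41% figures might be read as the study's false-positive risk. They are not. They need a sizeable net shift, in one direction, away from the limit. A pull towards the limit masks a difference instead.

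**The analysis could deal with it.** A reader might infer that the bias is beyond repair. That goes too far: if staff status and test familiarity were recorded, an analysis without those participants would be possible. The protocol does not mention recording either, and an analysis plan, which is not shown, could use them only if they were collected.

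**It is a pilot.** True, but its stated first aim is a local reference standard. Who may supply the measurements is a question of eligibility, which belongs in the protocol.

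**Conclusion.** The concern holds in limited form. As written, the eligibility criteria do not rule out study-team members or staff who perform, teach or interpret this test, and the primary outcome is a subjective response compared with a limit that they can be expected to know. Clinic-based recruitment makes their enrolment foreseeable, not certain.

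The size and direction of any bias are unknown. On the modest assumption of 3 informed participants among 29 and a 2 to 4 unit shift, the mean moves by less than a fifth of the stated precision and the test's error rate barely changes. The larger effects shown depend on shares that the documents do not support. No statement or figure in the protocol is shown to be wrong on this point. It is a cheap improvement.

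**What to change.** Add one exclusion criterion: members of the study team, and staff who perform, teach or interpret the field of binocular single vision test or the Hess test, may not be participants. Keep other hospital staff eligible. Record each participant's staff status and familiarity with the test on the case report form, so that a sensitivity analysis without familiar participants is possible.

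The cost is one line of eligibility text, two recorded items and a slightly smaller convenience pool. Relatives, other staff and volunteers remain available for the 32 places.

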A comprehensive medical history will be obtained from each participant through a structured interview. The investigator will specifically inquire about any history of facial trauma, ocular trauma, head trauma, ocular disease, ocular surgery or any systemic condition(s), documenting the nature, timing, and severity of any reported incidents. Particular attention will be paid to any previous ocular diseases and surgical interventions. All responses will be recorded in standardized case report forms, with detailed documentation of the type, date, and outcome of any reported conditions or procedures. Participants should not have any history of facial trauma, ocular trauma, head trauma, ocular disease, ocular surgery or any systemic condition(s). This thorough screening is essential to ensure participants meet the study criteria for establishing normative values.

2) *Near Visual Acuity Testing*

Near visual acuity will be assessed right eye and left eye monocularly & binocularly using a standard near vision chart held at 40cm from the participant's nose. Testing will be conducted under standardized lighting conditions with monocularly and binocularly and unaided. A measuring stick will be used to maintain the precise testing distance. The examiner will record the smallest line that can be read accurately, with participants required to achieve N6 or better to be included in the study. Any participant with near vision worse than N6 will be excluded from the study.

3) *Ocular Alignment Assessment*

A prism cover test will be performed at near of approximately 30cm from participant's nose to evaluate ocular alignment. The examiner will systematically assess alignment in five positions of gaze: primary gaze (straight ahead), right gaze, left gaze, up gaze, and down gaze. Measurements will be taken using loose prisms or a prism bar, with deviations recorded in prism diopters. Any deviation equal to or greater than 10 prism diopters in any of the five positions of gaze will result in exclusion from the study. The examiner will ensure consistent testing distance using a measuring stick and maintain standardized testing conditions throughout the assessment.

4) Extraocular Movement Testing

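### The alignment exclusion does not separate manifest from latent deviation, so an uncommon small manifest squint could enter the normative sample and record a full field

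*Protocol*

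**What the plan says.** The alignment rule stands in two places in Protocol section 2, and they agree. Exclusion Criterion 4 reads "Prism cover test at near (30cm) of equal or greater than 10 prism diopters at these positions of gaze", followed by five gazes. Research Procedures, item 3, says "A prism cover test will be performed at near of approximately 30cm from participant's nose to evaluate ocular alignment", and then "Any deviation equal to or greater than 10 prism diopters in any of the five positions of gaze will result in exclusion from the study". Neither place mentions manifest or latent deviation. Neither says which form of the prism cover test is used, and no separate cover-uncover step is described. Item 3 asks only for the size of the deviation to be recorded.

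The outcome measurement is in Research Procedures, item 7: "participants will press the buzzer if two distinct light stimuli are seen".

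Four other screens bear on the point:

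- History: "Any history of ocular disease" (Exclusion Criterion 2).
- Near acuity: "Right eye & Left eye monocularly, binocularly unaided near vision: worse than N6 at 40cm from participant's nose" (Exclusion Criterion 3).
- Eye movements: "Participants demonstrating overaction or underaction equal to or greater than 0.5 units in any direction will be excluded from the study" (Research Procedures, item 4).
- Hess chart: "Abnormal or asymmetry in pattern of extraocular muscle action in Hess chart test" (Exclusion Criterion 7). Item 6 of the procedures is broader and excludes on any Hess finding judged abnormal. Neither place gives a numeric limit.

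No test of suppression, fusion or stereopsis is described. Trained orthoptists do all the tests, at a single visit.

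**The concern.** A normative range for binocular single vision should come from people who have it. A size limit on the prism cover test asks how large a deviation is, not whether the eyes are jointly aligned when both are open. A latent deviation of 8 prism diopters that fusion controls is compatible with normal binocular single vision. A constant manifest deviation of the same size is a different state, yet both pass the rule as written.

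The endpoint makes this matter. Silence on the buzzer is scored as single vision. Someone with a manifest deviation who suppresses one eye need not see two lights, so can stay silent across the whole bowl. The result is a full field from a person without binocular single vision, and the outcome test cannot reveal it.

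The matter is hard to repair afterwards. There is one visit, and the protocol asks for the size of the deviation but not its type. Such a participant might not be identifiable at analysis.

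**Working it through.** **1. The plan's own figure.** The protocol's only calculation is the sample size, and it does not depend on the alignment rule. With SD 6, precision 2.2 and 95% confidence, n = (1.96 × 6 / 2.2)² = 28.57, rounded up to 29. The half-width at 29 is 1.96 × 6 / √29 = 2.18. Inflating for 10% dropout gives 29 × 1.10 = 31.9, so 32, or 29 / 0.90 = 32.2, so 33. The stated 29 and 32 reproduce closely enough. Here 2.2 is the precision of the **mean**.

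**2. Who gets past the screens.** Take a manifest deviation below 10 prism diopters and apply each screen.

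| Screen | Removes | Leaves |
|---|---|---|
| Prism cover test | 10 prism diopters or more | anything smaller, manifest or latent |
| Ocular history | squint already known and reported | undiagnosed squint |
| N6 in each eye | cases with clearly reduced near vision in one eye | cases reading N6 with each eye |
| Movement grading | over- or underaction of 0.5 or more | comitant deviation (similar in all gazes) |
| Hess chart | any plot judged abnormal | a plot the examiner judges normal |

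What remains is an undiagnosed, comitant, small manifest deviation with N6 in each eye and a Hess chart judged normal. Nothing described clearly detects that case.

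**3. How often.** The documents give no frequency. Let p be the assumed share of such cases among people who pass every other screen. The chance of at least one among 32 is 1 − (1 − p)³²:

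| p (assumed) | Chance of at least one |
|---|---|
| 0.5% | 15% |
| 1% | 28% |
| 2% | 48% |
| 5% | 81% |

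Given the screens in step 2, the lower rows have least support.

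**4. How much.** The documents give no effect either. For scale only, assume limits of mean ± 1.96 SD, 31 participants with SD 6, and one participant d units below their mean. The variance becomes (30 × 36 + d² × 31/32) / 31, the mean moves by d/32, and the lower limit moves outward by d/32 + 1.96 × (new SD − 6).

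| d (assumed) | New SD | Mean moves | Limit moves |
|---|---|---|---|
| 10 | 6.16 | 0.31 | 0.63 |
| 20 | 6.88 | 0.63 | 2.35 |
| 30 | 7.93 | 0.94 | 4.73 |

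The sampling error of such a limit at n = 32 is about 6 × √(1/32 + 1.96²/62) = 1.83, a 95% half-width of about 1.96 × 1.83 = 3.6.

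This table describes a **shrunken** field. The case left in step 2, when it suppresses, gives a full field, which may lie well inside the normal spread. The table therefore does not measure its effect, and nothing in the documents does.

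**The case against.** The strongest reply is that the rule does not stand alone. History, N6 in each eye, movement grading and the Hess chart come on top of it, and item 6 of the procedures excludes on any abnormal Hess finding, not only on asymmetry. The Hess test compares the two eyes, so a person who suppresses one might well fail it; that is general knowledge of the test, not protocol text. The two statements of the alignment rule agree, and one cut-off in a pilot of 32 can be defended. Most of this stands. It makes the case uncommon, but does not close the gap, because the Hess criterion rests on unquantified judgement and no step asks whether a deviation is manifest.

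Three stronger readings are tempting, and the documents do not support them.

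- A reader might infer that small squints enter freely because alignment is judged by size alone. The other screens would remove most of them.
- A reader might infer that vertical deviations below 10 prism diopters widen the range and need their own limit. A person seeing double over much of the field would have to volunteer as healthy, report no ocular history and pass the Hess chart. A deviation of 9 prism diopters is about 5 degrees (arctan 0.09), which may well be judged abnormal there. If the deviation is latent and fused, there is no double vision to shrink the field. The documents give no fusion limit from which to set a threshold.
- A reader might set a limit shift such as 2.35 against the planned precision of 2.2. That is not like for like, because 2.2 concerns the mean, which moves by only 0.31 to 0.94 in the illustration. The 2.35 also lies inside the limit's own sampling half-width of about 3.6.

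**Conclusion.** The concern holds in a limited form. Exclusion Criterion 4 and procedure 3 do not separate manifest from latent deviation, no suppression or fusion check is described, and the endpoint treats no report of two lights as single vision. One narrow kind of participant, as identified in step 2 of the working, could therefore enter the normative sample and, with suppression, record a full field without binocular single vision.

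This is a question of who belongs in the reference sample. It is not a demonstrated shift in the range. The chances of 15% to 48% for assumed shares of 0.5% to 2% show only that one case among 32 is not far-fetched on those assumptions. The direction and size of any effect on the limits remain unknown. The conclusion rests on reading the eligibility text literally and on the absence of any other described step that detects a manifest deviation. It is a specific, low-cost improvement and does not affect the sample-size calculation.

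**What to change.** At the cover test already planned, record for each tested gaze whether any deviation is manifest or latent, together with its size. Add to Exclusion Criterion 4 and to Research Procedures, item 3, as a further ground for exclusion: any manifest deviation on the cover test in any tested position of gaze. Keep the 10 prism diopter limit for latent deviations. No separate vertical limit is proposed.

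The change needs one line in each of the two places and one field on the case report form. The examiner and the visit stay the same. The downside is possibly an extra screen failure. If that person counted towards the 32, the margin of 32 − 29 = 3 would absorb the loss, provided no more than two others were lost.

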All examinations will be performed by trained orthoptists, with results recorded immediately in standardised documentation forms. The testing sequence will remain consistent across all participants, and any exclusion criteria met will be documented with specific measurements and observations.

As part of the clinical evaluation of participants during the analysis phase, access and extraction of data will be limited to TTS's NGEMR and Zeiss Forum Viewer. Clinical information collected for this study would include medical & ocular histories along with prior visual assessments documented by orthoptists.

Additionally, NEHR cannot and will not be used for research. Access of medical records for the purpose of data collection will also be limited to the period dated from 1 November 2025 to 31 October 2026. Clinical information/data collected will be done once off during, or retrospectively after the study visit.

Sample size calculation

This is a pilot study. Due to resource constraints, a total of 32 healthy participants will be recruited for this study.

Based on the literature, the standard deviation (SD) of normal values for the selected binocular single vision measure ranges from 5.3 to 6.9. Assuming an SD of 6 in our study, a sample size of 29 will allow us to estimate the mean of normal values with a precision of 2.2 at the 95% confidence level. We expect drop out rate to be no more than 10%, 32 participants will be sufficient.

References:

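### Does the field-of-single-vision test need a protocol rule for a run that ends without reported double vision?

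*Protocol*

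**What the plan says.** The measurement is described once, in Procedure 7 (Field of binocular single vision) under Research Procedures. Participants must "look and follow through the single light stimulus as it moves throughout the bowl". The one response that marks an edge is given next: "participants will press the buzzer if two distinct light stimuli are seen". The record is then made as follows: "Scores will be recorded and plotted on the recording sheet based on participants' responses during the test". No meridians, limit in degrees or value for a run without a press are given. The paragraph after Procedure 7 adds that trained orthoptists do every examination and enter results at once on standard forms, which are not shown.

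This measurement serves both outcomes. The first reads: "The primary outcome is the establishment of a normative range of field of binocular single vision measurements in Singapore adults". The second reads: "The secondary outcome is the comparison with the normal boundary of the established field of binocular single vision", meaning the 1974 boundary. Testing is done once, "with each participant completing all assessments in a single visit lasting approximately 60 minutes". The Sample size calculation says that "the standard deviation (SD) of normal values for the selected binocular single vision measure ranges from 5.3 to 6.9", and plans on SD 6, 29 evaluable participants and a precision of 2.2 for the mean. It does not name the measure or its unit.

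**The concern.** The only stated event that ends a run is reported double vision. The sample has been selected for small deviations, normal motility and a normal Hess chart, so some participants may follow the light to the end in some directions and never press the buzzer. If scores rest on responses, a run without one has no defined value. It could be left out, plotted at the limit of testing, or marked as at least that far.

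The choice could matter because the primary outcome is a range. If these runs are the widest, leaving them out removes the upper tail, and setting them to the limit compresses it. With one visit per participant, a reason for stopping that was not noted cannot be recovered later. The 1974 comparison would also depend on how edges were scored then, which the protocol does not report.

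**Working it through.** **The plan's own figure.** n = (1.96 × 6 / 2.2)² = 28.57, rounded up to 29. The stated sample size reproduces and does not bear on the gap.

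**Inputs.** From the Sample size calculation: SD s = 6 (range 5.3 to 6.9), n = 29, precision 2.2. Assumed, because the protocol is silent: a share c of runs ends without double vision; these are the widest; the true edge is normally distributed; there is one value per participant; SD 6 applies to that value; and the limits are mean ± 1.96 SD.

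**Formulas.** Let k be the standard normal quantile at 1 − c and φ the normal density.

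- Dropped: mean shift = −s·φ(k)/(1−c); SD = s·√(1 − k·φ(k)/(1−c) − (φ(k)/(1−c))²).
- Plotted at the limit (capped): mean shift = s·(k·c − φ(k)); second moment = s²·((1−c) − k·φ(k) + k²·c), and the SD follows by subtracting the squared mean shift.
- Shift of a limit = mean shift ± 1.96 × (SD − 6).

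**Worked case, c = 10%.** k = 1.2816 and φ(k) = 0.1755.

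- Dropped: mean −6 × 0.1755/0.9 = −1.17; SD 5.06; upper limit −1.17 + 1.96 × (5.06 − 6) = −3.01; lower limit −1.17 − 1.96 × (5.06 − 6) = +0.67.
- Capped: mean 6 × (0.12816 − 0.1755) = −0.28; SD 5.49; upper limit −1.28; lower limit +0.72.

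| Share | Dropped: mean | upper | lower | Capped: mean | upper | lower |
|---|---|---|---|---|---|---|
| 0% | 0 | 0 | 0 | 0 | 0 | 0 |
| 5% | −0.65 | −1.83 | +0.53 | −0.13 | −0.64 | +0.38 |
| 10% | −1.17 | −3.01 | +0.67 | −0.28 | −1.28 | +0.72 |
| 20% | −2.10 | −4.88 | +0.68 | −0.67 | −2.64 | +1.30 |
| 30% | −2.98 | −6.48 | +0.52 | −1.14 | −4.07 | +1.79 |
| 50% | −4.79 | −9.46 | −0.12 | −2.39 | −7.29 | +2.50 |

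**Against the study's precision.** The mean shift passes 2.2 only above about 21% dropped or 47% capped (18–24% and 43–51% over SD 5.3 to 6.9). The sampling half-width of an upper limit at n = 29 is 1.96 × 6 × √(1/29 + 1.96²/56) = 3.78. The upper-limit shift passes that above about 14% dropped or 28% capped.

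**Dependence on method.** With empirical percentiles, capping leaves the 2.5th percentile unchanged. Dropping lowers it by 0.13 at 5% and by 1.69 at 50%. The empirical 97.5th percentile falls under both: under capping by 1.89 at 5% and 4.07 at 10%, because it becomes the limit of testing itself. So the range does not move as a whole: its upper end comes in, and what its lower end does depends on the method.

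**The case for a change.** The best case for a change is that ending a run, and recording why it ended, is measurement procedure. A statistical analysis plan can treat a value as censored only if someone noted that it lay at the limit. The screening tests have distances and numerical cut-offs, and the main measurement has nothing comparable. One line and a tick-box would cost almost nothing.

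Part of this stands. The protocol is silent on the point, the arithmetic is right under its assumptions, and a note of why each run ended would be useful on the form. The case does not reach an error, for these reasons:

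- The larger shifts come from dropping runs, which the protocol nowhere proposes. An orthoptist plotting a field by hand has an obvious entry for a light followed to the end without doubling: the point where testing ended.
- A value at the end of the bowl is a legitimate reading if the range is meant for fields taken on this perimeter. Whether to treat it as censored, and how to report the counts, is usual material for the analysis plan, which may exist unseen.
- The sign is not secure. If one eye has lost the light, single vision at the end of a run is no longer binocular, and plotting it at the limit would overstate the field.
- If the unnamed measure is a summary score over directions, losing one direction does not remove a participant's value, and the model above does not describe the study.
- The recording form is not shown, so it cannot be said that it fails to capture these runs.

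**Conclusion.** No change to the plan follows. Procedure 7 leaves a detail unwritten, but it states no rule that gives a wrong result, and those doing the test can fill the gap sensibly. If runs without double vision do not occur, there is no effect. If 10% occur and are plotted at the limit of testing, the mean falls by 0.28 against a planned precision of 2.2, and the upper limit at mean + 1.96 SD falls by 1.28 against its own half-width of 3.78. Larger effects need a larger share, the dropping of runs, or an upper limit read as an empirical percentile, and the protocol establishes none of these. All the sizes rest on an assumed share, the widest runs being the affected ones, normality, and SD 6 applied to a measure whose unit is not given. How far the 1974 comparison is affected cannot be judged, because the end rule used then is not in the protocol.
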